## Appendix 1. Abbreviations

This following is a list of the abbreviations that may be used in this document.

Abbreviation	Term
%CDT	Percent Carbohydrate deficient transferrin relative to total transferrin
β-hCG	Beta-human chorionic gonadotropin
A1AT	Alpha-1-antitrypsin
Abs	absolute
ACC	acetyl-CoA carboxylase
AE	adverse event
ALT / SGPT	alanine aminotransferase / serum glutamic pyruvic transaminase
AST / SGOT	aspartate aminotransferase / serum glutamic oxalo-acetic transaminase
ATP	adenosine triphosphate
AUC	area under the curve (used when referring to PK)
AUC 24	area under the concentration-time curve from time 0 to 24 hours
AUC inf	area under the concentration-time curve from time 0 to infinity
AUC last	area under the concentration-time curve from time 0 to the time of the last quantifiable concentration
AUC tau	area under the concentration-time curve from time 0 to time t
AUDIT	Alcohol use disorders identification test
AUEC	Area under effect curve (used when referring to drug response)
CCI	
BID	bis in die
BLQ	below the limit of quantification
BMI	body mass index
BP	blood pressure
BUN	blood urea nitrogen
CAP TM	Controlled attenuation parameter
CK	creatine kinase
CK18-M30	cytokeratin-18-M30 sub-species
CK18-M65	cytokeratin-18-M65 sub-species
C max	peak or maximum observed concentration
CO 2	carbon dioxide (bicarbonate)
CPT-1	carnitine-palmitoyl transferase 1
CSA	clinical study agreement
CSR	clinical study report
CT	clinical trial
CTA	clinical trial application
CYP3A	Cytochrome P-450 3A
CCI	
D 2 O /  H 2 O	deuterium oxide / deuterated water
dB/m	decibels per meter
DBP	diastolic blood pressure
DCT	data collection tool
DDI	Drug-drug interaction
DILI	drug-induced liver injury
DMC	data monitoring committee
DNA	deoxyribonucleic acid
DNL	de novo lipogenesis
DPP-IVi	Dipeptidyl peptidase-IV inhibitors
DU	Dispensing Unit
EC	ethics committee
ECG	electrocardiogram
e-CRF	Electronic case report form
EDP	exposure during pregnancy
EDTA	edetic acid (ethylenediaminetetraacetic acid)

[figure not shown]
Abbreviation	Term
CCI	
eGFR	Estimated glomerular filtration rate
EIU	exposure in utero
ET	Early Termination
EU	European Union
EudraCT	European Clinical Trials Database
FA	flip angle
FDA	Food and Drug Administration
FFA	free fatty acid
CCI	
FIH	first-in-human
FPG	Fasting plasma glucose
FPI	Fasting plasma insulin
FSH	follicle-stimulating hormone
FU	Follow-up
GCP	Good Clinical Practice
GGT	Gamma-glutamyl transferase
GLDH	Glutamate dehydrogenase
GLP	Good Laboratory Practice
GLP-1r	glucagon-like peptide-1 receptor
HAE	Hypoglycemia
HbA1C	Glycated hemoglobin
HBsAg	hepatitis B surface antigen
HBV	Hepatitis B virus
HCC	Hepatic Cellular Carcinoma
HCV	Hepatitis C virus
HCV RNA	Hepatitis C virus genetic material (ie, Ribonucleic acid)
HCVAb	hepatitis C antibody
HDL-C	high density lipoprotein cholesterol
HIV	human immunodeficiency virus
HOMA-IR	Homeostatic model assessment of insulin resistance
hr	hour
CCI	
ht	height
IA	Interim Analysis
IB	Investigator's brochure
ICH	International Conference on Harmonisation
ID	identification
IND	investigational new drug application
INR	international normalized ratio
IOP	in- and out-of-phase
IP	investigational product
IRB	institutional review board
IRC	internal review committee
IRT	interactive response technology
IUD	intrauterine device
IWR	interactive web response
CCI	
kPa	kilopascals
LDL-C	low density lipoprotein-cholesterol
LFT	liver function test
LLN	lower limit of normal
LSLV	last subject last visit
LSM	Liver stiffness measure
CCI	
MCH	mean corpuscular hemoglobin
MCHC	mean corpuscular hemoglobin concentration

[figure not shown]
Abbreviation	Term
MCV	mean corpuscular volume
MDR1	multi-drug resistance protein-1
MDRD	Modification of Diet in Renal Disease
MEC	molar extinction coefficient
MedDRA	medical Dictionary for Regulatory Activities
MELD	model of end-stage liver disease
min	minute
MMRM	Mixed model repeated measure
MRI-PDF	Magnetic resonance imaging using proton density fat fraction acquisition
MRS	Magnetic resonance spectroscopy
MSDS	material safety data sheets
MTD	Maximum tolerated dose
N/A	not applicable
NAFLD	nonalcoholic fatty liver disease
NASH	Nonalcoholic steatohepatitis
CCI	
NGSP	National Glycohemoglobin Standardization Program
NOAEL	no observed adverse effect level
NOEL	no observed effect level
NSAIDS	Non-steroidal anti-inflammatory medications
NYHA	New York Heart Association
CCI	
OATP	organic anion-transporting polypeptide
CCI	
OEB5	occupational exposure banding 5
PBPK	physiologically based pharmacokinetic
PCD	primary completion date
PCSK9	proprotein convertase subtilisin/kexin type 9
PD	Pharmacodynamics(s)
PE	physical exam
CCI	
PI	Principal investigator
PK	pharmacokinetics
CCI	
PNPLA3	Patatin like phospholipase domain containing protein 3
pre-Q	Pre-qualification visit
ProC3	N-terminal pro-peptide of type III procollagen
ProC6	C-terminal fragment of $\alpha 3$ chain of procollagen type VI (also known as Endotrophin)
PT	prothrombin time
PTR	peak to trough ratio
Q12H	Every 12 hours (eg, dosing)
QC	quality control
QD	quaque die
QTc	corrected QT
RBC	red blood cell
RNA	ribonucleic acid
SAE	serious adverse event
SAP	statistical analysis plan
SBP	systolic blood pressure
SC	subcutaneous
SCr	serum creatinine
SEM	standard error of mean
SOP	standard operating procedure
SRSD	single reference safety document
SSID	Study-specific Subject identification
SUSAR	suspected unexpected serious adverse reaction

Abbreviation	Term
T 1/2	terminal half-life
T2DM	type 2 diabetes mellitus
TBili	total bilirubin
TEAE	Treatment-emergent adverse event
TG	triglycerides
Th17	T helper 17
THC	tetrahydrocannabinol
T max	time to reach maximum concentration
Treg	regulatory T
TZDs	thiazolidinediones
CCI	
ULN	upper limit of normal
US	United States
V	Visit
VCTE	Vibration-Controlled Transient Elastography
VLDL	very low density lipoprotein
V z /F	apparent oral volume of distribution
w/v	weight per volume
WBC	white blood cell
WOCBP	Women of childbearing potential
wt	Weight

## Appendix 2. Guidance to Investigators – Management of Individual Subjects With Decrease in Platelet Count

### Appendix 3. Guidance to Investigators – Management of Individual Subjects With Elevation in Fasting Serum Triglycerides

#### **Appendix 4. Guidance to Investigators – Capturing Details for Episodes of Hypoglycemia in Patients with T2DM**

The following checklist must be **completed by the site staff** during each outpatient visit to the site based on responses provided by the subject and where applicable, the adequate medical care provided to treat episodes of hypoglycemia.

Did the subject have any symptoms of hypoglycemia since their last visit to the site?

YES  NO

**If yes**, did the subject require assistance of another person to actively administer treatment for the event?  YES  NO

Did the subject exhibit any of the CNS symptoms of severe hypoglycemia? These include: memory loss, confusion, uncontrollable behavior, irrational behavior, unusual difficulty in awakening, suspected seizure, seizure, loss of consciousness.  YES  NO

Was blood glucose measured?  NO  YES

**If yes**, what was the result? \_\_\_\_\_  mmol/L  mg/dL; **and** did the result meet threshold for severe hypoglycemia?  YES  NO

Severe hypoglycemia is defined as subject was unable to treat him/her self AND subject exhibited CNS symptoms of severe hypoglycemia mentioned above AND *either* blood glucose when measured was  $\leq 49$  mg/dL (or 2.7 mmol/L) *or* blood glucose was not measured by clinical manifestation reversed by oral carbohydrates, subcutaneous glucagon or intravenous glucose.

**If no**, did symptoms resolve when treated with carbohydrates, or glucagon?  YES  NO

Did the event awaken the subject while asleep for the night?  YES  NO

What time did the hypoglycemic event start? What time did it resolve?

When was the last meal (of  $\geq 400$  kcals) consumed? \_\_\_\_\_ Date; \_\_\_\_\_ Time

When was the last dose of concomitant medication for glycemic control taken?

\_\_\_\_\_ Date; \_\_\_\_\_ Time

Were any actions taken?  YES  NO

**If yes**, dosing with investigational product – choose only **one** and enter details in concomitant treatment section.

No action taken  Trial drug stopped temporarily  Trial drug stopped permanently

Concomitant treatment dosing – choose only **one** and enter details in concomitant treatment section.

- No action taken  Dose increased  Dose reduced
- Drug stopped temporarily  Drug stopped permanently

Subject was: choose **all relevant options** and enter details in concomitant treatment section if applicable.

- Withdrawn from Trial
- Treatment given (specify details in concomitant treatment section)
- Other (specify):
- No Action

**Does Serious Criteria apply?** Serious is defined as fatal, life-threatening, inpatient hospitalization or prolongation of existing hospitalization, persistent or significant disability/incapability, congenital anomaly/birth defect, important medical event (ie, may jeopardize subject and may require medical/surgical intervention to prevent above listed outcomes).  YES  NO

Was the event a result of a study medication error?  YES / UNKNOWN  NO

**If yes**, complete Medication Error Log.

The following elements must be completed at the time the event resolves or at the end of the trial:

**Causality:** Is there a reasonable possibility the adverse event is related to trial treatment?

- YES / UNKNOWN  NO

**If no**, what is the most likely cause of the hypoglycemic adverse event? Choose **one** of the following:

- Concomitant treatment – drug or nondrug (specify);
- Other (specify).

If subject experienced symptoms of hypoglycemia, choose **all** that apply:

- Hunger  Palpitations  Blurred Vision  Headache  Tachycardia  Disorientation
- Dizziness  Tremulousness  Loss of Consciousness  Light Headedness  Irritability

Seizures  Sweats  Other (specify)

What type of treatment was administered?

Oral carbohydrates  YES  NO

Parenteral  YES  NO

Was a precipitating event identified?  YES  NO

**If yes, choose all relevant options** from the list below:

Missed Meal/missed snack  Diabetes Medication Error – wrong dose

Delayed Meal/delayed snack  Diabetes Medication Error – wrong time

Exercise  Other precipitating event (specify)

Comments

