##### **7.9.3.1.2. Definition and Severity Categorization of HAE**

Based on review of the subject completed diary at **each** visit to the site as well as results reported by the central laboratory, the investigator must assess the glucose values as well as any symptoms documented.

HAE is defined as **one** of the following:

1. **Asymptomatic hypoglycemia:** An event *not* accompanied by typical symptoms of HAE but a plasma glucose reading of  $\leq 49$  mg/dL (2.7 mmol/L) using sponsor-provided, plasma-referenced, home glucometers (or sponsor-identified central laboratory);
2. **Documented symptomatic hypoglycemia:** An event during which typical symptoms of HAE are accompanied *with* a glucose reading of  $< 70$  mg/dL (3.9 mmol/L) using sponsor-provided, plasma-referenced, home glucometers (or sponsor-identified central laboratory) **and** the clinical picture includes prompt resolution with food intake, subcutaneous glucagon, or intravenous glucose;
3. **Probable symptomatic hypoglycemia:** An event during which symptoms of HAE are *not* accompanied by a plasma glucose determination, but was presumably caused by a plasma glucose concentration of  $< 70$  mg/dL (3.9 mmol/L) using sponsor-provided, plasma-referenced, home glucometers (or sponsor-identified central laboratory) **and** the clinical picture includes prompt resolution with food intake, subcutaneous glucagon, or intravenous glucose.

**NOTE: Pseudo-hypoglycemia:** An event during which symptoms consistent with HAE are reported along *with* a plasma glucose reading  $\geq 70$  mg/dL (3.9 mmol/L) using sponsor-provided, plasma-referenced, home glucometers (or sponsor-identified central laboratory) *may* be reported as an adverse event (AE) of HAE but will **not** be considered as having met the protocol definition of HAE offered above.

*Each episode* of HAE must be characterized with respect to severity. In order to characterize the event as 'severe', **all three (3)** criteria below must be met:

1. The subject was unable to treat him/herself. Neurologic impairment, and not the age of the subject, is the explanation for why the subject could not treat him/herself and required the assistance of another person.
2. The subject exhibited at least **one** of the following neurological symptoms:
  - Memory Loss;
  - Confusion;
  - Uncontrolled behavior;
  - Irrational behavior;
  - Unusual difficulty in awakening;
  - Suspected seizure;

- Seizure;
  - Loss of consciousness.
3. Either:

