For each event, the investigator must pursue and obtain adequate information both to determine the outcome and to assess whether it meets the criteria for classification as an SAE (see [Section 8.2.3](#) below). In addition, the investigator may be requested by Pfizer Safety to obtain specific follow-up information in an expedited fashion. This information is more detailed than that recorded on the CRF. In general, this will include a description of the event in sufficient detail to allow for a complete medical assessment of the case and independent determination of possible causality. Any information relevant to the event, such as concomitant medications and illnesses, must be provided. In the case of a subject death, a summary of available autopsy findings must be submitted as soon as possible to Pfizer Safety. Any pertinent additional information must be reported on the CT SAE Report Form; additional source documents (eg, medical records, CRF, laboratory data) are to be sent to Pfizer Safety **ONLY** upon request.

As part of ongoing safety reviews conducted by the sponsor, any non-serious AE that is determined by the sponsor to be serious will be reported by the sponsor as an SAE. To assist in the determination of case seriousness, further information may be requested from the investigator to provide clarity and understanding of the event in the context of the clinical study.

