### **8.2.3. Serious Adverse Events**

A serious adverse event is any untoward medical occurrence at any dose that:

- Results in death;
- Is life-threatening (immediate risk of death);
- Requires inpatient hospitalization or prolongation of existing hospitalization;
- Results in persistent or significant disability/incapacity (substantial disruption of the ability to conduct normal life functions);
- Results in congenital anomaly/birth defect.

**Or** that is considered to be:

- An important medical event.

Medical and scientific judgment is exercised in determining whether an event is an important medical event. An important medical event may not be immediately life-threatening and/or result in death or hospitalization. However, if it is determined that the event may jeopardize the subject, **or** may require intervention to prevent one of the other AE outcomes, the important medical event should be reported as serious.

Examples of such events are intensive treatment in an emergency room or at home for allergic bronchospasm; blood dyscrasias or convulsions that do not result in hospitalization; or development of drug dependency or drug abuse.

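### The required Appendix 4 hypoglycemia checklist states a narrower important-medical-event rule (*and*) than Protocol Section 8.2.3 (*or*), so the two can classify the same event differently

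*Protocol*

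**What the plan says.** Protocol Section 8.2.3 lists the usual seriousness criteria and adds the important medical event. Such an event is to be reported as serious "if it is determined that the event may jeopardize the subject, or may require intervention to prevent one of the other AE outcomes". The *or* is emphasised in the text. The section also says that "Medical and scientific judgment is exercised in determining whether an event is an important medical event", and one of its examples is "blood dyscrasias or convulsions that do not result in hospitalization".

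Protocol Appendix 4 is the checklist for hypoglycemic episodes in subjects with type 2 diabetes. Its opening sentence makes completion by site staff compulsory at each outpatient visit, and Section 7.9.3.1.1 sends every episode to it for detail. It has a YES/NO question on seriousness with its own definition printed beside the boxes. The last item of that definition is the "important medical event (ie, may jeopardize subject and may require medical/surgical intervention to prevent above listed outcomes". The question carries no reference to Section 8.2.3.

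Protocol Section 8.1 requires the investigator to follow up each event, among other things "to assess whether it meets the criteria for classification as an SAE", and there it cites Section 8.2.3. It also provides that "any non-serious AE that is determined by the sponsor to be serious will be reported by the sponsor as an SAE".

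**The concern.** The two texts describe one regulatory category and differ in two ways. The connective changes from *or* to *and*, and intervention of any kind becomes medical or surgical intervention. Each change makes the checklist narrower. The narrower text is the one in front of the person filling in the form.

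Seriousness has operational consequences. Under the table in Protocol Section 8.1, every SAE goes to the sponsor's safety group within 24 hours of awareness, and no non-serious AE does. Under SAP Section 7.2, the IRC receives SAE and death listings with narratives drawn from the safety database. An event ticked non-serious could miss both until someone corrects it. This would happen in the diabetic subjects, for whom the protocol promises a standardized capture of hypoglycemia (Section 1.3.2).

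**Working it through.** No sample size, power or error rate is involved and the plan states no figure to reproduce. The check compares the definitions.

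**Step 1: the other seriousness criteria.** Death, threat to life, hospitalization or its prolongation, disability, and congenital anomaly appear in both Section 8.2.3 and Appendix 4. An event meeting any of these is serious under both texts. Any disagreement is confined to events whose only route to seriousness is the important-medical-event criterion.

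**Step 2: the two conditions.** Let J mean that the event could endanger the subject, and I that it could need intervention to avert one of the other outcomes. Section 8.2.3 requires J or I. Appendix 4 requires J and I.

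| J | I | Section 8.2.3 | Appendix 4, read literally |
|---|---|---|---|
| yes | yes | serious | serious |
| yes | no | serious | not serious |
| no | yes | serious | not serious |
| no | no | not serious | not serious |

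Section 8.2.3 makes 3 of the 4 combinations serious and Appendix 4 makes 1. They disagree in 3 − 1 = 2 of 4. The restriction to medical or surgical intervention can also move an event out of the first row, if the only intervention in view is neither.

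**Step 3: can such an event arise?** Section 7.9.3.1.2 counts seizure among the neurological symptoms of a severe episode, in a subject who "could not treat him/herself and required the assistance of another person". Where glucose was not measured, reversal by oral carbohydrate satisfies the third severity requirement. A seizure at home that ends this way, without admission, fits the convulsion example in Section 8.2.3. On the checklist, the answer depends on whether the person completing it thinks medical or surgical intervention might have been needed. Either answer can be defended on the form's wording, so the form does not secure the classification that Section 8.2.3 points to. This does not make every severe episode serious. Section 8.3 keeps severity and seriousness apart.

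**Step 4: what depends on the answer.**
- 24-hour reporting (Protocol Section 8.1): depends on seriousness.
- SAE listings and narratives to the IRC (SAP Section 7.2): depend on seriousness.
- Subject-level TEAE listing to the IRC (SAP Section 7.2): does not. A treatment-emergent episode appears there either way.
- Hypoglycemia summaries (SAP Section 6.6.1): do not. They use subjects with an event, event rate, number of events per subject, and a separate rate for severe events.
- Efficacy analyses: do not.

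**The case against.** The strongest reply is that the checklist does not decide seriousness. Section 8.1 ties classification to Section 8.2.3, Section 8.4.1 sends all SAEs through the general route with no special rule for hypoglycemia, and Appendix 4 is titled as guidance for capturing details. The important-medical-event decision rests on medical judgment, and the sponsor can upgrade an event. A reader might infer from the mismatch that serious hypoglycemic events will be recorded as non-serious and that hypoglycemic SAEs will be under-counted. The documents do not support that, for these reasons, and this part of the reply stands.

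Two further points also stand. First, the checklist asks whether intervention *may* be required. An episode with neurologic impairment that a relative ends with food need not be answered NO, because glucagon or intravenous glucose might have been needed. Second, the table counts combinations, not events. In hypoglycemia the two conditions largely overlap, and an event that might need intervention to avert death or admission will usually also endanger the subject. It would be wrong to read two of four, or two of the three that Section 8.2.3 makes serious, as a proportion of events lost.

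The reply does not remove the inconsistency. If Section 8.2.3 governs, a compulsory form still prints a different rule beside its seriousness question. Judgment is exercised within a definition, and here there are two. Sponsor upgrade comes after the site's decision, whereas the reporting clock is 24 hours from awareness.

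**Conclusion.** The mismatch is certain. Both texts are current, and neither redaction nor amendment history explains it. The compulsory checklist is narrower than the governing definition, and the two disagree in two of the four combinations of its conditions. The consequence is a risk, not an established outcome: checklist and SAE classification may differ, the 24-hour report may be late, and an event may be missing from the SAE listings and narratives that the IRC sees.

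This rests on site staff applying the printed definition as written, and it is limited to hypoglycemic events that meet one condition of this criterion and no other seriousness criterion. How many there would be cannot be derived from the documents. The IRC would still see treatment-emergent episodes in the TEAE listing. The efficacy results and the planned hypoglycemia counts, rates and severity summaries do not change.

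**What to change.** Reconcile Appendix 4 with Section 8.2.3. The simplest way is for the checklist's seriousness question to refer to Section 8.2.3 and drop its own definition. If a definition is kept on the form, join the two conditions with *or*, as Section 8.2.3 does, and remove the medical/surgical restriction. Make the same correction in any CRF material that repeats the checklist wording. The documents do not show whether such material exists.

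The cost is one line in an appendix, plus the matching change in any such CRF material. The downside is that a few more hypoglycemic events may be reported as SAEs.

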1 VERSION HISTORY

C1171002 protocol Amendment 2 (version: 03-Oct-2017) remains effective for this amended version of the SAP.

The original SAP is amended to correct typographic errors, to reflect a number of clarifications, to aid in more clear derivation and reporting of endpoints, and types of analyses. Major changes from the original SAP are summarized in Table 1.

Table 1 Summary of Major Changes in SAP Amendments

SAP Version	Change	Rationale
1	Not Applicable	Not Applicable
2	
 a. Section 3.4.2: Definition of permitted to be nonfasted and mandatory fasted laboratory/ pharmacodynamics parameter b. Creation of Section 4.5: Stratum Reassignment c. Section 5.3: LLQ and ULQ reporting rules 	
 a. Fasting status impacts numerical results b. Instances have been encountered wherein subjects were randomized to incorrect strata, in error. Section is describing how to handle such cases during reporting c. Clarification on how to derive results which are either below LLQ and above ULQ – specifically for pharmacodynamic parameters
	CCI	
	
 f. Section: 6.4: Revisions made to subset analysis of subjects randomized in Taiwan 	
 f. Considering the limited number of subjects randomized across sites in Taiwan (n=6), generation of descriptive summary was deemed non-informative as at most each arm will have less than 2 subjects as randomization is applied at a country-level; as such, supplemental outputs restricted to subjects from Taiwan will not be generated (approach endorsed by

	
g. Adding Total Bilirubin as 1 of the liver function tests
 
h. Appendix 2.4: Compliance calculation
 
i. Appendix 2.2.6: Additional safety figures
 
j. HOMA-IR, CCI [REDACTED] are unit less
 
k. Adding summary statistics for %CDT and AUDIT questionnaire
 
l. Appendix 2.31: Additional safety figures
	
Taiwan-FDA on 01Nov2018 based on input sought by Pfizer-Taiwan)
 
g. Throughout the SAP, Total Bilirubin (TBILI) added as part of the Liver Function Test group; omitted originally in error
 
h. Compliance calculation revised to utilize details from oral dosing CRF page (and not drug accountability CRF page) as the former accounted for any missed or dropped doses (where as the drug accountability page was strictly based on pill count returned) – thereby permitting a more accurate assessment of compliance via use of details captured on oral dosing CRF page for “active bottles” only
 
i. Addition of set of figure reporting triglycerides, ApoC3, FPI and FPG levels over time for subjects presenting at any time post-randomization with fasting serum triglycerides level ≥ 600 mg/dL
 
j. Appendices 2.2.10, CCI [REDACTED]: Indicate respectively that HOMA-IR, CCI [REDACTED] re unit-less parameters
 
k. Appendix 2.3.3 and 2.3.4: Both parameters added because they were omitted originally in error.
 
l. Appendix 2.3.1: Addition of set of figure reporting platelet count, INR and aPTT over time for subject presenting at any time post-randomization platelet count lower than $100,000/\text{mm}^3$ (ie, $100 \times 10^3/\text{mm}^3$)

--	--	--

